1 PROTOCOL SUMMARY

1.1 SYNOPSIS

Title:**Study Description:**

Electrophysiologic studies of cognition in epilepsy patients

In this study, we seek to study how brain activity contributes to the generation of actions, emotions, memories, and other thought processes. To do that, we propose to examine brain activity recorded in patients undergoing neurosurgical interventions for treating epilepsy. Specifically, we leverage the fact that intractable epilepsy patients are surgically implanted with electrodes that allow recording the brain's electrical activity. Each electrode provides a readout of electrical activity in a different brain area, and therefore a way to measure brain activity in a very precise way, both anatomically and temporally, something that is very difficult to achieve otherwise in human subjects. We combine these recordings of electrical activity with tasks designed to test different aspects of behavior and thought, such as memory, decision-making, spatial navigation, etc. These take the form of short computer games that the patients will play while their brain activity is recorded using the clinically implanted electrodes. We will subsequently analyze the brain data, together with the patients' behavior and information about the location of each electrode, to derive information on how brain activity in different brain areas is related to behavior. In some cases, we will use special electrodes that allow very precise examination of neural activity (i.e. examine activation of single neurons, compared to large populations of neurons using other approaches) or use small amounts of electrical currents to stimulate specific brain areas to test their contribution to behavior. This will provide us with a more detailed understanding of the neurobiology of thought and provide causal observations of the contributions of individual brain areas. In a subset of patients that are clinically determined to undergo treatment resection, we will collect tissue samples for molecular analyses. This combination of electrophysiological recordings and behavioral tasks provide a unique opportunity to understand the contribution of brain processes to normal thoughts and behavior, as well as how these are affected in disease states (i.e. epilepsy, depression).

Objectives* :

Primary Objective:

Study the neurophysiological basis of human cognition and actions.

Endpoints*:

The primary endpoint of this research is to investigate electrophysiological correlates of human cognitive and perceptual processes. The approach involves the analysis of the brain's electrical activity during computer-controlled cognitive/perceptual tasks, to determine how behaviors that occur during these tasks correlate with changes in electrical activity measured inside the human brain and on the scalp.

The secondary endpoint of this research is to examine changes in neural activity and behavior in response to neurostimulation.

The tertiary endpoint of this research is to characterize the genetic and molecular composition of human brain tissue to reveal important information about genetic differences in epileptic tissue and correlate electrophysiological and molecular biological measures to brain function and clinical diagnoses.

The knowledge gained from these experiments will further our understanding of the brain's electrical activity and its relation to human cognition and disease. This increased knowledge base may lead to insights regarding better treatments for cognitive deficits and to improve epilepsy surgery and other therapies for seizure and other disorders.

Further, uncovering the electrophysiological signatures of cognitive function through functional mapping, which enables the surgeon to avoid the resection of brain regions that could be especially crucial to cognitive function, may be improved, reducing the risk of post-surgical cognitive impairment following resection.

Epilepsy patients undergoing invasive monitoring.

[figure not shown]
Mount Sinai Health System Hospitals and Epilepsy outpatient clinics.

Study Population:**Description of Sites/Facilities Enrolling Participants:****Study Duration*:****Participant Duration:**

An initial period of 10 years, to be extended as data collection continues.

Length of duration of intracranial EEG recordings in the Epilepsy Monitoring Unit (EMU; typical EMU stays range between 5-14 days) plus up to 12 months post-discharge.

1.2 SCHEMA

Study Design:

Research will be conducted at Mount Sinai West and Mount Sinai Hospital. Patients will be identified and recruited in either of these settings. Electrophysiological recordings will take place during patient stay in the Epilepsy

Monitoring Unit (EMU) of either site. Select tasks may need to be collected before hospital admission or after discharge; these will be carried out either in person during a patient visit to the hospital or remotely through a computer screen in the patients' preferred setting (i.e. at their homes) through a computer browser.

Mount Sinai may act as the coordinating institution across several research institutions involved in research. In such case, all sites will carry out research following all NIH and IRB guidelines and regulations. We will establish a research reliance and/or data transfer agreements with Mount Sinai as necessary.

1.3 SCHEDULE OF ACTIVITIES

Patients will participate in the study for the duration of their hospitalization (typically 5-14 days in the EMU; 1 day for participation in placement of the microelectrodes during surgery). In some cases, patients will be asked to complete one or several remote behavioral tests (computer games) before they are admitted or after they are discharged from the hospital. In the case of pre-operative testing, the available time window will occur between consenting and EMU stay, typically a few weeks. Consent will take place preoperatively or on surgery day. If patients undergo resective surgery and consent to research use of resected tissue, this portion will happen at the time of resection, determined on clinical grounds. For post-operative testing, patients will be asked to carry out behavioral testing one or several times over the 12 months following EMU discharge.

	Pre-operative	Surgery Day	Epilepsy monitoring unit stay (typically 5-14 days)	Resective surgery (if applicable)	Post-discharge (up to 12 months)
Informed Consent	X	X			
Demographics			X		
Clinical history	X	X	X		X
Obtain tissue				X	
Outcome Evaluation					
Quality of Life Questionnaire			X		X
Task Administration	X		X		X
Adverse Events Reporting			X		X

2.1 STUDY RATIONALE

The study aims at understanding the neural substrates of language, attention, motor control, emotion and memory processing; as well as developing techniques to improve neurosurgical treatment of seizures and brain abnormalities. These approaches will assess the functional connectivity and communication between cortical regions involved in human cognitive processing. It will provide neuroanatomical, electrophysiological neurostimulation and behavioral information about the neural circuits involved in decision-making, attention, motor control, emotion and memory. This will ultimately help us improve clinical treatment of neurosurgical patients.

2.2 BACKGROUND

Although one can crudely measure the human brain's electrical signals by recording from the scalp, the ability to observe and measure oscillations generated in local regions of the brain requires recordings taken from electrodes implanted in the brain (i.e., invasive EEG, or iEEG recording). Such iEEG recordings are often clinically required in the surgical treatment of severe medication-resistant epilepsy (i.e., seizure disorders that are not controlled by standard drug therapies). For these patients, surgery is potentially curative; the goal in planning surgery is to precisely localize the brain areas responsible for seizure activity. This can be accomplished by monitoring iEEG recordings over a period of several days to several weeks.

Intracranial EEG monitoring furthermore enables the study of single-neuron activity using hybrid "micro-macro" electrodes that contain additional microwire bundles exiting from the tip of the standard clinical electrodes. This minor modification provides a rare and important opportunity to study the human nervous system as a single-cell resolution in awake, behaving humans. This paradigm has led to key insights into epileptic seizure generation and propagation, as well as human cognition.

In addition, electrical brain stimulation is a routine procedure in the EMU for localization of brain function and is frequently performed in patients with intracranial electrodes. By studying how electrical stimulation elicits changes in oscillatory activity related to epilepsy or cognition, we may be able to causally discern the specific brain circuits involved. Electrical stimulation also provides the opportunity to measure changes in neurotransmitter concentration via voltammetry techniques that have been utilized in rodents for 25 years, and human subjects more recently, and can assess how critical neurotransmitters such as dopamine, serotonin, and norepinephrine fluctuate in relation to human cognitive performance.

iEEG recordings therefore offer a rare and valuable opportunity to record neurophysiological activity directly from the human brain, compare these results with those from animal models and to extend these insights into uniquely human cognitive capabilities (for example in decision-making or abstract reasoning). iEEG recordings have already been used to greatly enhance our knowledge of the physiology of human cognition by allowing investigating local cortical dynamics in an awake human, how different cortical areas interact to generate cognition and actions, to assess the formation and propagation of seizures, and to carry out causal interrogations of brain activity ([name] 2018, Sani 2018, Helfrich 2018, Kahana 1999, Fried 2014, Parvizi 2013, Desmurget 2009).

In addition, resective surgeries, which are a possible treatment outcome post-iEEG evaluation, offer a possibility to recover human tissue for subsequent molecular analysis and characterization. This offers unique possibilities to characterize the genetic and molecular composition of human brain tissue, which could reveal important

information about genetic differences in epileptic tissue, and allow correlating electrophysiological and molecular biological measures.

2.3 RISK/BENEFIT ASSESSMENT

2.3.1 KNOWN POTENTIAL RISKS

EMU patients will be under standard neurology and nursing care with video/medical monitoring in the EMU. Note that these patients typically have their medications tapered during their stay in order for them to have seizures, which is the goal of the clinical monitoring. In the event of a seizure, standard protocols will be followed on the unit. Again, patients are supposed to have multiple seizures during this stay in the EMU. A member of the study team will always be present during the testing required for this study, including testing that involves stimulation.

- Cognitive testing: all cognitive and memory tests are designed to be minimally difficult. Some subjects may find the tests to be stressful, tiring, or boring. Cognitive testing will not interfere with their epilepsy monitoring or treatment. Standard medical care and safety protocols during EMU admission will not be altered by participation in this study. If an intervention is medically required due to the occurrence of seizures or post-ictal complications (including but not limited to the administration of sedating or anticonvulsant medications, resuscitative measures including supplemental oxygen, or patient restraint for safety in the setting of post-ictal agitation), the cognitive testing will be aborted and/or deferred until a time when the patient's medical condition permits continuation of the testing. Procedures to mitigate risks of cognitive testing: session times will be minimized, and assessments may take place over more than once session, if needed and appropriate. Participants may also take breaks, as needed. Subjects have the right to refuse to answer questions they feel are too distressing, as well as to terminate any one part or the whole of their participation at any time.
- Single neuron recordings: we will use augmented macro-micro electrodes that include, in addition to the macro contact sites routinely used for clinical recordings, micro contact filaments to allow electrophysiological recordings that can isolate individual neurons. There is no additional risk of intracerebral hemorrhage or tissue injury compared with the standard clinical macro electrodes. There are no reports of any ill effects from these FDA-approved electrodes for clinical EEG recording. Recordings from the microelectrode filaments that protrude from the macro electrode shaft do not interfere with the usual clinical recordings and have the potential to significantly improve some aspects of mapping seizures and cognition. Every study examining the design and safety of such micro-macro depth electrodes has found them to be as safe and effective as standard depth electrodes for intracranial monitoring (House 2006, Van Gompel 2008, Waziri 2009, Hefft 2013, Misra 2014, Carlson 2018). Their use requires no extra surgical procedures. Procedures to mitigate risks of single neuron recording: we will only use single-unit recording electrodes in locations targeted for clinical reasons. The locations and number of sEEG electrodes will therefore be based on clinical necessity and will not be changed due to participation in this study. Only a subset of sEEG electrodes (typically 1-4) will be replaced by macro-micro electrodes.
- Brain stimulation: we do not anticipate any significant increase in risk, since we will be using FDA-approved electrodes and stimulating according to clinical protocols. Stimulation will be carried out using macro electrodes only, even if the patient consented to microelectrode implantation. It is possible that brain stimulation could produce a seizure that causes injury. We will monitor the occurrence of seizures producing injury in all enrolled patients. Patient safety will be tracked by the PI and research staff in real time and reported to the Mount Sinai IRB according to the guidelines in HRP-214. Procedures to mitigate stimulation testing risks: to minimize the risk of triggering a seizure through stimulation, we will limit stimulation to levels routinely used by the clinical team for functional mapping (≤ 6 mA). Stimulation testing will only be carried out once the patient has been cleared

for explantation by the clinical team, to minimize risks of elicited seizures prolonging the patients' medical stay. Stimulation will only occur using macroelectrodes.

- Privacy: the risk of loss of private information, however small, is always present when PHI is shared by a patient, as well as when data is shared among study personnel and collaborators. However, we will take every precaution to prevent this. Each participating patient will be assigned a unique identification number and there will be no reference personal identifiers in any subsequent publication. All personal identifiers will be destroyed upon completion of the research and the required storage period. Data files will be stored on a secured server, which will be password-protected and access to data files will be given only to IRB approved research personnel. The main risks of audio and video recordings performed in this protocol are associated with patient privacy. Patients will be fully informed that their face and voice will be identifiable to the team members analyzing the data. While recordings will only be associated with a participant's study ID, it is not possible to fully de-identify facial images. Procedures to mitigate privacy risks: The risk of disclosure of PHI will be adequately conveyed to participants in the informed consent document for this study. The study investigators and research staff will abide by all policies and procedures set forth by Mount Sinai and in accordance with Good Clinical Practices with respect to the proper storage and transfer of PHI and other subject data. Only the minimal amount of patient information, including that which is personally identifiable, will be accessed in the conduction of this study.
- Tissue resection: tissue resection will be carried out adhering to clinical protocols, with all research activities being carried out on the resected tissue. Therefore, no additional risks are estimated.
- Unforeseeable risks: this study may involve risks that are currently unknown and unforeseeable. Procedures to Mitigate Unforeseeable Risks: All new information, including new risks and that which may affect a person's decision to continue study participation, will be disclosed as it becomes available.

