Brain Stimulation: Electrical brain stimulation is a routine procedure in the EMU for localization of brain function and is frequently performed in patients with intracranial electrodes. We plan to use similar focal currents, using macroelectrodes to stimulate the brain, during cognitive tasks to help localize and define cognitive networks. The patient's baseline performance on specific tasks will be established on trials without stimulation and compared to trials with stimulation in specific regions and statistically analyzed. For stimulation, we may employ the stimulation hardware routinely used for clinical mapping (e.g. Nicolet cortical stimulator) or an equivalent research device (e.g. ATLAS Stim Headbox - High Density, part number: 31-0601-0132) using identical stimulation parameters as specified below. The electrical current will be kept at or below the same safe levels as used in standard clinical cortical mapping. Safety limits have been established for decades (McCreery, et al. 1990; Gordon et al., 1990, Shannon 1992). Here, we will apply stimulation while subjects perform cognitive tasks at levels far below the safety limits identified by histological analysis for stimulation protocols (McCreery, et al. 1990; Gordon et al., 1990). Stimulation studies will be performed using currents not exceeding 10mA, below the accepted safety limits for charge density (Shannon 1992), and in line with previous studies. There is no evidence that stimulation of the type to be performed in this study causes any patient risk. The only significant change to the patient's routine in the proposed studies is that brain stimulation will be performed for longer periods and sometimes in different locations than required for standard evaluation. Patients will be asked frequently if they would like to continue or stop testing, and testing will be halted at any signs of patient discomfort or fatigue. Electrical stimulation also provides the opportunity to measure changes in neurotransmitter concentration via voltammetry techniques that have been recently developed for safe use in human subjects (Kishida 2018).

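### Research stimulation has two current ceilings: 6 mA as the seizure mitigation in section 2.3.1 and 10 mA in section 4.1

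*Combined protocol and SAP*

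**What the plan says.** Section 2.3.1 (Known Potential Risks, brain stimulation) accepts that stimulation could cause a seizure leading to injury and lists countermeasures. The first, whose stated aim is "to minimize the risk of triggering a seizure through stimulation", reads "we will limit stimulation to levels routinely used by the clinical team for functional mapping (≤ 6 mA"). The section's overall risk statement is "we do not anticipate any significant increase in risk, since we will be using FDA-approved electrodes and stimulating according to clinical protocols".

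Section 4.1 (Overall Design, Brain Stimulation) makes three relevant statements about the same macroelectrode stimulation:

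- A qualitative limit: "The electrical current will be kept at or below the same safe levels as used in standard clinical cortical mapping".
- A numerical limit: "Stimulation studies will be performed using currents not exceeding 10mA, below the accepted safety limits for charge density". The sentence cites a charge-density model and adds that this agrees with earlier studies.
- A declared departure from routine, presented as the only significant one: "brain stimulation will be performed for longer periods and sometimes in different locations than required for standard evaluation".

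Section 4.1 also says that the clinical stimulator and the research stimulator will share the parameters set out later in that section. The only current value that follows is 10 mA.

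**The concern.** The two numbers limit the same quantity in the same procedure, and both stand in the current text. Someone setting the stimulator from the design section would find 10 mA and no mention of 6 mA. An ethics board judging risk from section 2.3.1 would find 6 mA and no mention of 10 mA.

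What is at stake is the basis for the risk assessment. Section 2.3.1 expects no significant increase in risk partly because stimulation follows clinical protocols. That reason does not reach currents above the clinical level the section itself names. Participants typically have their medication tapered (2.3.1), may be minors from age 10 (5.1) and are told to expect no direct benefit (2.3.2). Section 4.1 already lets duration and location go beyond routine practice, so current is the parameter the plan undertakes to hold at clinical level.

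**Working it through.** No power or sample-size formula applies. The check is to compare the two limits and then ask whether other text reconciles them.

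**Inputs**

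| Source | Limit | Ground given |
|---|---|---|
| 2.3.1 | at most 6 mA, described as the routine clinical mapping level | seizure risk |
| 4.1, numerical sentence | at most 10 mA | charge density; previous studies |
| 4.1, qualitative sentence | at or below clinical cortical mapping levels, no figure | established safe practice |

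**Size of the gap**

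- Ratio of ceilings: 10 / 6 = 1.67.
- Width of the disputed band (above 6, up to 10 mA): 10 − 6 = 4 mA.
- Share of the range allowed by the 10 mA figure: 4 / 10 = 40%.

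**A test case.** Take 8 mA:

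- 8 ≤ 10, so it meets the numerical limit in 4.1.
- 8 > 6, so it breaches the mitigation in 2.3.1.
- If clinical mapping means at most 6 mA, as 2.3.1 states, it also breaches the qualitative limit in 4.1.

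Section 4.1 is therefore inconsistent within itself once 2.3.1 supplies the clinical figure. Its account of what differs from routine points the same way: it declares longer duration and different locations, but not higher current.

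**Is there a reconciling statement?**

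- Neither section assigns the figures to different electrodes, devices, tasks, regions or patients. Both concern macroelectrodes.
- The amendment history (10.2) logs tissue collection and added stimulation hardware for version 2 and does not mention current. This is weak evidence, since it lists only that version's changes.
- The protocol deviations section (10.1.9) contains adverse-event text and no deviation rule, so it does not settle how an 8 mA session would be classed.

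**What cannot be computed.** The documents give no relation between current and seizure probability. The ratio of 1.67 compares two limits and does not measure risk.

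**The case against.** The strongest reply is that both figures are upper bounds and can be met together: any current up to 6 mA satisfies every sentence in both sections. On this reading 10 mA is an outer bound for tissue safety and 6 mA a tighter bound for seizure risk. Section 4.1 also ties current to clinical mapping levels, so a session above 6 mA would not comply with that section as a whole.

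The first part stands as a description of safe conduct, but the text does not present 10 mA as a mere reference bound. It says the studies will be performed at currents up to that value. The second part also stands: 8 mA meets only the 10 mA figure in 4.1, not every sentence there. That makes the 10 mA figure harder to defend, because it conflicts with the text around it.

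A further reply is that other protections remain. One is staffing: "A member of the study team will always be present during the testing required for this study, including testing that involves stimulation". Another is timing: stimulation waits until the patient is cleared "for explantation by the clinical team, to minimize risks of elicited seizures" that would prolong the stay. There are also EMU nursing care and video monitoring, real-time safety tracking, halting at signs of discomfort or fatigue, termination on an adverse event (4.4) and an independent medical monitor (10.1.6). These are real and reduce the consequence, but none of them sets a current limit.

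Finally, the documents do not show which figure was intended, so the choice belongs to the clinical team and the IRB. That is fair, and the remedy leaves room for it.

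**Conclusion.** The concern holds. The design section's only numerical ceiling permits currents up to 1.67 times the level that the risk section promises as its seizure mitigation, and nothing in the document reconciles the two. This is a wrong safety threshold as written, not a missing detail, and it must be corrected.

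The conclusion rests on two readings: that both sentences govern research stimulation through macroelectrodes, which the text supports, and that the 6 mA in 2.3.1 is the clinical mapping level to which 4.1 refers. The conflict between the two numbers stands without the second reading; only the inconsistency inside 4.1 depends on it.

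The finding is limited to a patient-safety limit. It does not show that currents above 6 mA will be used, and it changes no sample size, endpoint or analysis.

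**What to change.** State one ceiling in both sections.

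- **Default:** in section 4.1, replace the 10 mA limit with 6 mA. This agrees with the seizure mitigation in 2.3.1, with the clinical-mapping sentence in 4.1 and with the declared departures from routine. If the sponsor wants to keep 10 mA in the text as a tissue-safety reference, it should say explicitly that 6 mA governs.
- **If the clinical team and IRB want 10 mA:** remove the 6 mA commitment from 2.3.1, justify currents up to 10 mA for seizure risk and not only for charge density, and revise the risk statement there. In 4.1, revise the clinical-mapping sentence and add higher current to the declared departures from routine.

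In either case, check that the consent form gives the same figure; its pages were not available for this review.

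The default costs a one-figure wording amendment and the consent-form check. It needs no additional patients and no change to any analysis.
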